Hypoglycemia questionnaires	X														X					X
Scale of Borg ⁷		X																		X
HE supply form	X				X				X				X	X	X	X	X	X	X	X

*Acceptable deviation for weekly planned visits (visits 2-13) is +/-1 day from the planned date, monthly visits (visits 14-22) is +/- 3 days from the planned date.

¹ Demographic indicators: age, gender, race.

² Date of diagnosis of diabetes, clinical symptoms.

Therapy for diabetes: insulin (type, dosage), insulin+oral hypoglycemic therapy (type, dosage), sulphonylurea (type, dosage), glinide (type, dosage), metformin (dosage), TZD (dosage), DPP4 (type, dosage), GLP1 (type, dosage), other type of treatment.

Complications of diabetes: cardio-vascular diseases, strokes, retinopathy, neuropathy, nephropathy, diabetic foot, other.

³ Concomitant diseases (cardio-vascular diseases, hypertension, eye diseases, vascular diseases of the brain, gastrointestinal tract diseases, respiratory diseases, liver and bile ducts diseases, kidney diseases, blood diseases, etc.)

⁴ General blood test: hemoglobin, leukocytes (+formula), erythrocytes, thrombocytes, ESR.

⁵ Clinical blood test: crude protein, cholesterol, lipids of low and high density, triglycerides, ALT, AST, KPhK, creatinine, GFR.

⁶ Urine analysis: color, transparency, relative density, traces of protein, sugar in urine, ketone bodies.

⁷ Scale of Borg (scale of individual perception of physical training) is part of Information card (Appendix 8).

Study period and parallel group study design allows achieving of primary end point.

The control group indicators should be coordinated with the indicators of patients in active group. The following should be taken into account when active group is being formed: correspondence of BMI and baseline HbA1c. The decision on whether the patient is included in active or control group is made by the doctor.

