The full study lasts 12 months. Patients in active group are monitored intensely every 7 days. After first 13 weeks assessment of weight and health condition are conducted on a monthly basis (see Table 7.1 as reference). For patients in control group all examinations should be conducted every three months (see Table 7.2 as reference).

In order to collect data for the primary and secondary end points (6.3, 6.4) in control group assessment of all indicators will be conducted at trial' start and then the patients will be invited to the doctor by the end of 3rd, 6th, 9th and 12th months (see table 7-2).

Patients from active group fill out the Information card before they enter the study (**Appendix 8**) and Registration form (**Appendix 9**). Patients fill out the Information card at the end of the study as well (including assessment of individual perception of physical exercises using the scale of Borg).

It is necessary to discuss with a patient the patient's ability and readiness to make changes in his/her lifestyle when a doctor makes a decision to include a patient in the study.

The program of active weight reduction includes group classes with the team of doctors:

- Nutritionist in regards to healthy nutrition (**Appendix 10**)
- TE doctor/fitness trainer in regards to physical activity (**Appendix 11**)
- Psychologist in regards to motivation and education (**Appendix 12**) and self-control (**Appendix 13**)
- Endocrinologist (**Appendix 13**).

Classes for the patients in active group are conducted one time a week in the first 12 weeks with the following monitoring once a month in the next 36 weeks. Total period of observation is one year (48 weeks). Detailed classes description is in the **Appendix 1**.

Patients from control group do not take part in the group classes but their indicators are collected during the routine visits to doctors (a doctor will invite a patients following the plan of visits, table 7-2).

All prescribed procedures assigned by the doctors should meet the medical needs of the patients and should be conducted according to the recommendations of the Russia Association of Endocrinologists.

The specialists will use their professional skills in order to achieve the purposes and outcomes and they are responsible for taking into account the guidelines of the RAE.

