6.2 Exclusion criteria

Patients fulfilling any of the following criteria are not eligible for inclusion in this study:

1. Pregnant or nursing (lactating) women, where pregnancy is defined as the state of a female after conception and until the termination of gestation.
2. Type 1 diabetes
3. Proliferative retinopathy, hemorrhage and disinsertion of retina
4. Renal impairment: serum creatinine >1.5 mg/dL, creatinine clearance < 40 ml/min and/or proteinuria.
5. The lack of ability to perform the physical exercises due to the orthopedic or cardiovascular disorders *
6. Chronic alcoholism, acute alcoholic intoxication

* - the criterion is applicable only for the active group.

7 Population determination for statistical analysis

- All enrolled patients: all patients who signed informed consent for inclusion in the study. The population will be used for the disposition data summaries and listings.
- Safety Population: all patients of the active group included in the study, who started participating in the lifestyle correction program, and all patients of the

control group for whom the observation was started. The population will be used to summarize adverse events and other safety parameters.

- Full Analysis Set (FAS): all patients who provided baseline data and data to evaluate at least one efficacy parameter after the onset of observation. The population will be used for efficacy analyses.
- Per Protocol Set (PP): all FAS patients who did not have any major protocol deviations. The population was used to analyze the primary endpoint (sensitivity analysis).

The patient can be excluded from the Per Protocol Set for the following reasons:

- did not attend more than 3 consecutive classes in the active group;
- missed at least 50% classes of the program;
- did not provide data for the estimation of the primary endpoint.

8 General considerations

The latest available estimates before the start of the program for the active group and data from the Visit 1 for the control group will be used as the baseline values for the analysis of quantitative efficacy and safety parameters. The baseline visit is Visit 2 (Week 1) for the active group and Visit 1 for the control group.

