The Last observation carried forward (LOCF) approach will be used in FAS population (primary analysis) to impute missing values of the efficacy parameters using the last available measurement after the initiation of the studied program for active group and after the start of observation for the control group.

Descriptive statistics for quantitative variables will include mean, standard deviation, median, quartiles, minimum and maximum, and the number of observations. The maximum number of decimal places reported shall be 4 for any summary statistic.

Qualitative data will be presented in terms of the number of patients providing data at the relevant time point (n), frequency counts and percentages. Percentages will be calculated using n as denominator and will be presented to one decimal place.

9 Patient disposition

The following data on patient disposition will be provided for the All enrolled patients set:

- Number and proportion of patients in each population for statistical analysis;
- The number and proportion of patients enrolled in the study, as well as attended each study visit;
- Number and proportion of patients who discontinued prematurely (indicating the reasons for the discontinuation), as well as those who completed the study;
- Number and proportion of eligible patients.

10 Demographic and other baseline characteristics

The following demographic and other baseline characteristics will be tabulated and presented descriptively:

- Demographic characteristics (age, sex, race);
- Medical history (number (proportion) of patients with concomitant diseases);
- Duration of type 2 diabetes (months);
- Clinical manifestations of diabetes at the time of diagnosis and at the time of enrollment (the number (proportion) of patients with each of the clinical manifestations);
- Concomitant complications of diabetes (number (proportion) of patients with concomitant complications);
- Baseline body weight, height, body mass index;
- Baseline HbA1c% and fasting blood glucose (mmol/l).

Age will be calculated as the number of complete years between the date of birth of the patient and the date of signing the informed consent.

The body mass index (kg/m²) at each visit will be calculated as the ratio of body weight (kg) to the square of height (m) (Visit 1).

The duration of the disease will be calculated in years as (the date of the primary diagnosis of type II diabetes - the date of the informed consent + 1) / 365.25.

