12.1 Treatment response variables

Descriptive statistics for body weight (kg), body mass index (kg/m²), waist circumference (WC, cm) and waist to hip ratio (WHR), HbA1c%, fasting blood glucose (mmol/L), lipid profile (cholesterol, triglycerides, LDL, HDL) values together with absolute and relative (%) changes from baseline, as well as systolic and diastolic blood pressure (mmHg) values together with absolute changes, will be tabulated by visit for the FAS population. In addition, descriptive statistics for the above variables and their changes will be tabulated for visits corresponding to Weeks 12, 24, 36, 48, after the imputation of missing values using LOCF approach.

The primary endpoint - the number (proportion) of patients for whom body weight decreased by at least 5% compared to baseline values at 12 months of observation - will be analyzed in FAS (LOCF), additionally the primary endpoint analysis will be repeated in the Per Protocol Set (PP).

The number and proportion of patients with a decrease in body weight of at least 5% compared to the baseline values at 12 months of observation will be tabulated based on available measurements and based on imputed (LOCF) values in the FAS population. The results for the primary endpoint will also be presented by centers.

To compare proportions between groups, the main analysis of the primary endpoint will be carried out using logistic regression with the calculation of the odds ratio with 95% CI. In order to adjust for the potential confounding factors, potentially influencing factors such as age, gender, baseline value of the body mass index, the duration of the disease, baseline level of HbA1c will be included in the regression model.

As part of the sensitivity analysis, the primary endpoint will be analyzed without imputation of missing values using the GEE (Generalized Estimating Equations) method, taking into account the correlation of the repeated measurements at different visits for each patient.

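### Every planned primary-endpoint analysis depends on follow-up data after assignment, which active patients can supply about 10 weeks before controls, and none counts an assigned patient without follow-up as a non-responder.

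*SAP*

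**What the plan says.** **Entry to the set.** SAP section 7 defines the FAS as "all patients who provided baseline data and data to evaluate at least one efficacy parameter after the onset of observation" and adds: "The population will be used for efficacy analyses". The wording is the same for both groups. Having started the programme is a condition of the Safety Population, not of the FAS. The all-enrolled set is described as "all patients who signed informed consent for inclusion in the study. The population will be used for the disposition data summaries and listings".

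**Analyses of the primary endpoint.** SAP 12.1 analyses 5% weight loss at 12 months in the FAS with LOCF and repeats it in the Per Protocol Set, which SAP 7 draws from the FAS. The GEE sensitivity analysis without imputation is listed as an FAS table in SAP 18.1.

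**Baseline and LOCF.** SAP section 8 takes the latest value before programme start as the active group's baseline value and states: "The baseline visit is Visit 2 (Week 1) for the active group and Visit 1 for the control group". Missing active-group values are filled "using the last available measurement after the initiation of the studied program for active group".

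**Visits.** The note under the active-group schedule (Protocol section 7) reads: "Acceptable deviation for weekly planned visits (visits 2-13) is +/-1 day from the planned date". That table marks weight, fasting glucose and blood pressure at every visit. For controls, Protocol section 10 says: "For patients in control group all examinations should be conducted every three months".

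**Dropout.** Protocol 10.1 treats an active patient as having left the study after three successive missed classes in the first 12 weeks. Protocol section 8 and SAP section 6 expect about 20% dropout overall and none among controls.

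**The concern.** The primary set is selected on something that happens after the doctor has chosen the group, and the chance to meet the condition comes much earlier in one group. In an open study of a lifestyle programme, failing to take up the programme is part of what happens when it is offered. If such patients disappear from the denominator, the active response rate describes those who took it up rather than those assigned to it. A control who is never seen after Visit 1 also disappears, and that exclusion acts in the other direction. Because every planned efficacy analysis uses the FAS or a subset of it, the report would not show whether the primary result depends on this selection.

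The entry rule also accepts data on any one efficacy parameter. A patient with a later blood pressure or glucose value but no weight after the start enters the FAS, yet LOCF has no weight to carry forward and the primary outcome is undefined.

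**Working it through.** The plan gives no figure for this point. Its sample-size statement supplies the denominators of 100 and 30. It gives no SD and no responder rates, so it offers no expected response to work from. The steps below are timing read from the documents, then denominator arithmetic on assumed counts.

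**1. Earliest entry to the FAS**
- Active: Visit 2 (Week 1) is the baseline visit, so the first clearly post-baseline visit is Visit 3, about Week 2.
- Control: the first return is at the end of month 3. With 4-week months, 3 × 4 = Week 12.
- Gap: 12 − 2 = 10 weeks. It is 11 weeks if Visit 2 data may count, which is unclear because onset of observation is not defined for the active group.

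**2. The never-starter**
- A patient who attends no class meets the termination rule after the third missed class.
- That patient has no measurement after programme start, so nothing qualifies for the FAS and LOCF has no source.
- No other rule in the SAP would count the patient as a non-responder.

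**3. Effect on the active group** (assumed: R responders among 100 assigned, k never-starters, all non-responders; controls 3/30)
- FAS rate = R/(100 − k); all-assigned rate = R/100; ratio of the two = 100/(100 − k).
- Crude OR = active odds ÷ control odds. Control odds = 3/27 = 0.111.

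| R | k | FAS rate | OR, FAS | OR, all assigned |
|---|---|---|---|---|
| 40 | 0 | 40.0% | 6.0 | 6.0 |
| 40 | 5 | 42.1% | 6.55 | 6.0 |
| 40 | 10 | 44.4% | (40/50)/0.111 = 7.2 | (40/60)/0.111 = 6.0 |
| 40 | 20 | 50.0% | 9.0 | 6.0 |
| 30 | 10 | 33.3% | 4.5 | 3.86 |
| 50 | 10 | 55.6% | 11.25 | 9.0 |

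The row with k = 20 is an outer case, in which all of a 20% active dropout consists of never-starters.

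**4. Effect on the control group** (assumed: m non-responding controls with no visit from month 3 on; active 40/100)
- Control rate = 3/(30 − m).
- m = 1: 10.3%, OR 5.78. m = 3: 11.1%, OR (40/60)/(3/24) = 5.33. m = 6: 12.5%, OR 4.67.

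**5. Both together:** k = 10 and m = 3 give (40/50)/(3/24) = 6.4, against 6.0 for all assigned.

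**6. Scale against sampling error**
- For 40/100 against 3/30, SE of log OR = √(1/40 + 1/60 + 1/3 + 1/27) = 0.64.
- The shift from 6.0 to 7.2 is ln(1.2) = 0.18, or 0.18/0.64 = 0.28 of one SE.

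**The case against.** Much of the case on the other side stands.

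- **The exclusion of never-starters is not written down.** A reader might infer that the SAP removes anyone who does not begin the programme. It does not say so: that condition belongs to the Safety Population. The exclusion follows only when the termination and LOCF rules are read together with the FAS definition.
- **Active patients do not clearly qualify at the first weekly visit.** SAP 8 makes that visit their baseline. The gap is then about 10 weeks, which is still large.
- **The asymmetry does not all favour the programme.** An active patient who leaves at week 3 stays in the FAS with an early weight carried forward, and will probably count as a non-responder. Dropping early-lost, non-responding controls also lowers the odds ratio.
- **The counts are assumptions, and the shift is modest.** Protocol section 10 asks the doctor to discuss readiness for change before inclusion, and active patients need ophthalmologist and cardiologist clearance. Both may limit no-shows. In the main illustration the shift is well under one SE.
- **The losses would be visible.** SAP 9 reports the numbers in each population and the reasons for discontinuation, and Listing 4.1 gives body weight for all enrolled patients. A non-responder count could be rebuilt, but it would not be pre-specified.
- **There is no randomisation to preserve.** The doctor chooses the group, so making all assigned patients the primary set is a debatable choice of estimand.

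These points limit the claim about direction and size, and they weaken any case for replacing the primary set. They do not answer the central gap: no planned efficacy analysis counts an assigned patient who has no follow-up.

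**Conclusion.** The point holds as a gap in the planned analyses. Entry to the FAS depends on follow-up after assignment, the opportunity comes about 10 to 11 weeks earlier for active patients, and neither the per-protocol nor the GEE analysis brings back those left out.

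A reader might go further and conclude that the FAS inflates the primary odds ratio. The documents do not support that as a general statement. The two exclusions oppose each other, and the plan gives no counts for either. Net inflation follows if no control drops out, as the plan assumes, some active patients never start, and those patients are non-responders. Under those conditions, 10 never-starters in 100 move a 40% response to 44.4% and the odds ratio from 6.0 to 7.2. With 3 controls also lost, the result is 6.4. The effect could change the conclusion only if the result is borderline.

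The FAS rule also leaves the primary outcome undefined for any patient admitted without a weight after the start. That follows from the text and needs no assumed counts, although it should be uncommon because weight is scheduled at every active-group visit.

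**What to change.** Keep the FAS analysis and make three changes to the SAP.

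1. Pre-specify an analysis of the primary endpoint in all patients assigned to a group who have a baseline weight. For the active group, baseline is the latest value before programme start, which for never-starters is Visit 1; for controls it is Visit 1. Count patients with no later weight as not achieving 5% loss, in both groups, and report the result beside the FAS result.
2. Apply the same non-responder rule to FAS patients with no weight after the start, so that the primary outcome is defined for everyone in the set.
3. Define onset of observation for the active group and state whether Visit 2 data can count as post-baseline.

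The data are already collected, so the cost is SAP wording and one further table. Response rates may be slightly lower in either group. The odds ratio may move either way, because early-lost controls also become non-responders.

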7.6 Risks and benefits

The risk to subjects in this trial will be minimized by compliance with the eligibility criteria and study procedures, close clinical monitoring.

There are no therapy changes or innovations in this study. The drug therapy administration is carried out strictly in accordance with the approved instructions for medical use, only with the registered indications and in accordance with appropriate clinical practice.

The study is designed to establish for patients with T2DM and obesity the reduction of the body weight, improvement of glycemic and lipid metabolism, and reducing blood pressure level. We expect that the study can improve a QoL and reduce diseases complications in the study populations. Nvs survey on hypoglycemia will be used to assess the quality of life in patients (**Appendix 2**).

8 Population

The study is expected to include approximately 100 patients with T2DM and obesity. It is planned to have 100 patients in the active group who will be on active life style management; the control group will be 30 patients who will be matched with active group in terms of their indicators. Both groups will receive standard drug therapy for diabetes.

The control group should match the active group. The following criteria should be taken into account (criteria of inclusion and exclusion): match in BMI (<30; ≥30) and baseline HbA1c (<7.5; ≥7.5). The decision to include a patient into active or control group should be made by a doctor.

Drop-out of patients is expected for about 20% of patients compared with the originally included population. The drop-out criteria is three in a row missed group classes in the first 12 weeks of the study in active group.

The drop-out in control group is not expected.

Patients will be distributed among two participating research centers.

The study will be executed in two sites, the [REDACTED] in Moscow and the [REDACTED] in Kazan. The adult patients with T2DM (men and women at the age of more than 18 years) will be under the observation if they need in the active weight loss according to the physician's decision and if a doctor decides that the active approach is necessary.

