10.1 Withdrawal of Consent form

Patients may voluntarily withdraw consent to participate in the study for any reason at any time.

Withdrawal of consent occurs only when a patient does not want to participate in the study anymore and does not want any further visits or assessments and does not want any further study related contacts and does not allow analysis of already obtained biologic material.

The patient from active group will be considered as terminated the study provided he/she missed three group classes in a row in the first 12 weeks.

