5.2 Secondary endpoints

- Body weight decrease expressed in percents and in absolute values in comparison with baseline at 3, 6, 9, 12 months of observation;
- Number (proportion) of patients achieved weight loss of at least 5% in comparison with baseline at 3, 6, 9 months of observation;
- Number (proportion) of patients achieved weight loss of at least 10% in comparison with baseline at 3, 6, 9, 12 months of observation;
- Changes of HbA1c and FPG levels expressed in percents and in absolute values;
- Number (proportion) of patients achieved decrease of HbA1c by at least 0.5% in comparison with baseline;
- Number (proportion) of patients achieved HbA1c $\leq 7\%$ at 12 months of observation;
- Blood pressure changes in absolute values in comparison with baseline;
- Number (proportion) of patients achieved decreasing of systolic and diastolic blood pressure levels by at least 5 mmHg in comparison with baseline;
- Changes of lipid profile (cholesterol, triglycerides, LDL, HDL) expressed in percents and in absolute values in comparison with baseline;
- Changes of waist circumference, waist-to-hip ratio;
- Changes of BMI;
- Assessment of changes by Hypoglycemia Perspectives Questionnaire for active group patients, as well as by perceived exertion rate with Borg scale.

6 Patients enrolled in the study

The study planned to include 130 patients with type 2 diabetes and obesity. In the active group, it was planned to recruit 100 patients, who will actively participate in lifestyle correction program; the control group will consist of 30 patients with T2DM, matching the active group patients by main parameters, who will to be managed in accordance with routine clinical practice for T2DM patients. The control group should be comparable to the active group with regard to the core baseline parameters.

When forming the control group, the following criteria should be taken into account (inclusion criteria in the study): BMI (<30 ; ≥ 30) and baseline HbA1c (<7.5 ; ≥ 7.5). The decision about inclusion of a patient in the active or control group is left at the discretion of the treating physician.

Dropout of 20% from initially enrolled population was considered by the study design. The patient's dropout from the study is defined as three consecutively missed classes within the first 12 weeks of observation in the active group. No dropout in the control group is assumed.

Patients are distributed between two sites participating in the study.

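### The Per Protocol attendance rules select patients in the active group only, so PP is a weak robustness check, and no planned analysis counts a missing week-48 weight as non-response

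*SAP*

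**What the plan says.** SAP section 7 defines the PP set as "all FAS patients who did not have any major protocol deviations" and uses it for a sensitivity analysis of the primary endpoint. A patient can be excluded for three reasons: "did not attend more than 3 consecutive classes in the active group"; "missed at least 50% classes of the program"; and "did not provide data for the estimation of the primary endpoint". Only the first names a group.

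The drop-out rule is stated three times. SAP section 6 defines it as "three consecutively missed classes within the first 12 weeks of observation in the active group". Protocol section 8 says: "The drop-out criteria is three in a row missed group classes in the first 12 weeks of the study in active group". Protocol section 10.1 treats an active patient as having ended the study if "he/she missed three group classes in a row in the first 12 weeks". SAP section 6 plans for 20% drop-out and assumes none in controls. Protocol section 10 says that controls do not attend the classes.

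Under SAP sections 8 and 12.1, the main analysis is a covariate-adjusted logistic regression in the FAS with LOCF. There are two sensitivity analyses: the same analysis in PP, and a GEE analysis without imputation.

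**The concern.** A sensitivity analysis should put the main result under strain. This PP set removes active patients for something that happens after baseline, poor attendance, and has no counterpart rule for controls. Patients who stop attending a weight programme may well be those who lose less weight. If so, PP moves the estimate towards the hoped-for result, and agreement between PP and FAS gives false comfort. The covariates (age, sex, BMI, disease duration, HbA1c) are baseline characteristics and do not measure adherence, so adjustment cannot be relied on to remove the selection.

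The other planned analyses leave the same question open. Protocol section 10 aims for a 5% loss in the first three months and maintenance afterwards. LOCF can therefore carry an early loss forward as a 12-month success for a patient who left. The GEE uses observed visits only, so a leaver is not a failure at month 12. The tabulation on available measurements leaves missing patients out of the denominator.

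**Working it through.** **1. Which group each PP reason can reach**

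| Reason (SAP 7) | Active | Control |
|---|---|---|
| More than 3 consecutive classes missed | yes | no, by its wording |
| At least half of the classes missed | yes | no, controls have no classes |
| No data for the primary endpoint | yes | yes, but no control drop-out is assumed |
| Other major protocol deviation (general definition) | yes | yes |

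**2. The plan's own figure.** The plan gives no expected size for PP. The only relevant figure is 20% drop-out, and 80/(1 − 0.20) = 100 agrees with the active group size. I therefore take 20 of 100 active patients as excluded and none of the 30 controls.

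**3. Shift between FAS and PP.** Let r be the response rate in retained active patients, e the rate in excluded active patients and c the control rate. The documents give none of these; all are assumptions.

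- FAS active rate = 0.8r + 0.2e
- PP active rate = r
- Shift = 0.2(r − e)
- Crude OR = [p/(1 − p)] / [c/(1 − c)]

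With r = 50%, PP is 50% throughout. Its OR is 9.0 at c = 10% and 5.7 at c = 15%.

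| e | FAS rate | PP minus FAS | FAS OR, c = 10% | FAS OR, c = 15% |
|---|---|---|---|---|
| 0% | 40% | +10 points | 6.0 | 3.8 |
| 10% | 42% | +8 | 6.5 | 4.1 |
| 20% | 44% | +6 | 7.1 | 4.5 |
| 50% | 50% | 0 | 9.0 | 5.7 |
| 70% | 54% | −4 | 10.6 | 6.7 |

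For e from 0 to 20%, the shift is 4 to 8 points at r = 40% and 8 to 12 points at r = 60%.

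With no difference in the FAS (10% in each group) and all 10 active responders among the 80 retained, PP gives 10/80 = 12.5% and OR = (0.125/0.875)/(0.10/0.90) = 1.29.

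If the third reason also removes control non-responders, the gap narrows. Start from 3 responders among 30 controls. Removing 3 non-responders gives control odds 3/24 and a PP OR of 8.0. Removing 6 gives odds 3/21 and a PP OR of 7.0.

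**4. Counting missing weights as non-response.** Suppose the 20 excluded patients are also those without a week-48 weight. The 80 retained give 40 responders. LOCF credits the leavers with 0 to 4 more (0 to 20%), so FAS-LOCF is 40 to 44%. Non-response imputation gives 40/100 = 40%, and PP gives 40/80 = 50%.

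**5. The threshold gap (a separate matter).** Drop-out needs three consecutive missed classes within 12 weeks. The PP rule needs more than 3, so at least four, and names no window. I counted all attendance patterns over 12 weekly class dates, assuming independent misses. A longest run of exactly three with under half missed has this probability:

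| Miss rate | Run of 3 or more | Run of 4 or more | Exactly 3, under half missed |
|---|---|---|---|
| 10% | 0.9% | 0.1% | 0.8% |
| 20% | 6.5% | 1.2% | 4.5% |
| 30% | 18.9% | 5.3% | 8.9% |

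The last column is the patients who meet the drop-out rule but neither PP attendance reason. Real misses are likely to cluster, so these figures show scale only.

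**The case against.** Selecting adherent patients is what a PP set does, and when only one group has a programme the asymmetry is built in. PP is not the main analysis. The GEE keeps FAS patients with data, and the SAP also reports population sizes, class attendance and protocol deviations, so a reader can see how selective PP is. All of this stands. It is why the point concerns how PP is labelled and what is missing beside it, and is no reason to drop PP.

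A reader might go further and infer three things that the documents do not support.

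- *The PP rules remove only active patients.* They do not say so. The third reason and the general definition have no group limit. Zero control drop-out is a planning assumption, not an exclusion rule.
- *PP is certain to favour the programme.* That requires excluded patients to respond less often. Equal response gives no shift, and better response reverses it.
- *The threshold mismatch causes the bias.* It works the other way: more than 3 excludes fewer active patients than three would, so it makes PP less selective.

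The mismatch may also matter little in practice. A patient treated as having ended the study may have no 12-month weight and be excluded for the third reason anyway. The SAP does not say whether an LOCF value counts as data for that reason, so this cannot be settled.

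Non-response imputation has a limit too. It addresses missing data, not the PP definition, and if drop-out occurs only in the active group it penalises only that group. It is a conservative bound, not a neutral estimate.

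**Conclusion.** The point holds in a limited form. Both attendance exclusions act only on the active group, and the third is expected to fall mainly there. Agreement between PP and FAS is therefore weak evidence of robustness.

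Under the assumed rates (r = 50%, e = 0 to 20%, one fifth of active patients excluded, no control excluded), PP raises the active response rate by 6 to 10 points. The crude odds ratio rises from 6.0–7.1 to 9.0 at 10% control response, or from 3.8–4.5 to 5.7 at 15%. The direction is likely rather than established, and the planned odds ratios are adjusted, so these sizes are illustrative.

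The firmer finding needs no assumed rates: FAS-LOCF, GEE and PP all leave out the case in which a patient without a week-48 weight is a failure. The main analysis itself is not affected.

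The mismatch between three and more than 3 is a plain inconsistency in the text, independent of the bias argument.

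**What to change.** 1. Add to SAP section 12.1 a sensitivity analysis of the primary endpoint on all patients with a baseline weight. Count anyone without a week-48 weight as a non-responder in both groups, and use the same logistic model and covariates. Present it as the robustness check.
2. Label the PP analysis as supplementary, describing the effect in attenders.
3. State in SAP section 7 whether an LOCF value counts as data for the third PP reason.
4. Reconcile the PP missed-class rule, including its time window, with the drop-out rule in SAP section 6 and protocol sections 8 and 10.1, so that one definition is used or the difference is explained. Which number applies is for the sponsor to decide.

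The cost is some SAP wording and one extra table, plus a protocol clarification if the drop-out rule is the text that changes. The added estimate will be conservative and will mainly penalise the active group if drop-out occurs there; the report should say so.
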